Effects of Leukine[®] on mobilization of white blood cells will be determined by CBC with differential at screening, baseline Day 1 and on days 4, 6, 9, 11 and 15 of the treatment schedule (i.e. placebo or Leukine[®] at 250 mcg /m²/day/SC for 5 days/ week for three weeks), and at the 45 and 90 day follow-up visits. Vital signs, injection site review, and adverse event monitoring will be performed at each treatment visit. Complete metabolic panels (CMP) will be performed at screen, and on days 4, 9, 15, 45, and 90 days after initiation of GM-CSF treatment (Table 1 below summarizes the time-table of procedures for the entire study). The follow up MRI at the end of the treatment phase will provide information on any adverse changes in the brain, such as vasogenic edema and microhemorrhage. The DSMB will review all available data after each group of 5 Leukine[®]-treated and 5 placebo subjects have finished the treatment phase and determine whether the remainder of the subjects (5 Leukine[®]-treated and 5 placebo) will continue to receive the same full recommended dose (250 mcg/m²/day/SC).

HYPOTHESIS 1. Recombinant human GM-CSF, Leukine[®], will be tolerated by, and safe to use in mild-to-moderate AD patients.

SPECIFIC AIM 2. To test the hypothesis that Leukine[®] treatment will improve cognition in mild-to-moderate AD patients (*Secondary Endpoint*).

A battery of cognitive tests will be performed at baseline and at approximately 15, 45, and 90 days after initiation of Leukine[®] treatment to determine whether any AD features reverse during or after Leukine[®] treatment compared to subjects receiving placebo. Primary cognitive tests will include the Mini Mental State Examination (MMSE) and the ADAS-cog (Alzheimer's Disease Assessment Scale-cognitive subscale).

HYPOTHESIS 2. Leukine[®] treatment in adults with mild-to-moderate AD will improve cognition as measured primarily by MMSE total score and ADAS-cog total score.

SPECIFIC AIM 3. To investigate whether Leukine[®] treatment has an effect on Medial Temporal Lobe Atrophy (MTA) in mild-to-moderate AD patients (*Tertiary Endpoint*).

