- Should the potential subject have a screening blood pressure (BP) of more than 150 systolic or 95 diastolic, they will need to be under the care of a primary care provider for management of hypertension.
- The BP will have been well-controlled on a stable regimen for at least two months prior to study entry.
- The screening BP will be no greater than 160 systolic or 95 diastolic. (This limit will apply to all and any BP measurements during the screening process.)

Management Criteria during the treatment phase of the study:

- Should blood pressure rise above 165 systolic or 95 diastolic, the patient will be removed from the study.

- The subject’s hypertensive regimen may be adjusted by the primary care provider during the study as needed.

Sample size considerations:

Due to the well documented safety history of Leukine® ([1], attached as Appendix D) combined with additional patient information from the USF site, we believe that a sample size of 20 patients per research arm is adequate to assess our Primary Endpoint of measuring safety. Although the Moffitt BMT study was not specifically designed to distinguish the cognition of patients receiving GM-CSF plus G-CSF from those receiving G-CSF alone, it was possible to glean conclusions about the cognitive benefit of GM-CSF or G-CSF treatment. The study found highly significant improvement (p<0.01) in the scores of 19 patients receiving GM-CSF plus G-CSF, compared to patients receiving only G-CSF.

A Power analysis showed the following results:

Here is a table of the sample size needed per group with alpha at .20 and power at .60 for independent samples t tests:

Effect size	1 tailed test	2 tailed test
.3 - small	27	53
.5 - medium	10	20
.8 - large	4	8
1.22 – observed from BMT	3	4

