Because the effect size of cognition improvement was so high with the BMT patients, that analysis provides clinical information as a reference to choose an appropriate sample size of AD subjects to receive GM-CSF as a potential cognition enhancer (one of our Secondary Endpoints). Essentially, only 3-4 subjects are needed for a power of 0.6. Therefore, the November 15, 2013 protocol proposed to recruit a total of 40 mild-to-moderate AD patients of either sex in a placebo-controlled protocol, with 20 subjects (10 Leukine®-treated and 10 placebo) recruited at the UCD site and 20 subjects (10 Leukine®-treated and 10 placebo) recruited at the USF site. However, with the revisions from the April 6, 2016 DSMB report, the revised protocol also removes active recruiting from the USF site, due to the retirement of [name], and the remaining trial participants will be recruited at the UCD site.

The study will have two arms with subjects assigned in permuted blocks examining placebo and full recommended Leukine® dose. As mentioned above, in the trial subjects who have thus far received Leukine® at the University of South Florida, there were no serious adverse events reported by patients receiving either half dose or full dose Leukine® using the same methods proposed by this protocol. Therefore we will be starting patients at the full FDA-recommended Leukine® dose (250mcg/m²/day SC). To assure that safety concerns of treating a novel population (AD patients) with GM-CSF are addressed, initially 5 subjects will be treated for 5 days/week for 3 weeks with Leukine® and 5 participants will be given placebo, followed by a DSMB review of the CBC+diff blood data, the MRI data, and the physical exam and adverse event monitoring at the end of the treatment phase. The DSMB will then recommend whether the dosage should be continued for the subsequent 5 Leukine® treatment subjects and 5 placebo controls or whether the Leukine® should be adjusted to a half dose. Recruitment and treatment initiation will be timed to allow for the DSMB interim assessments before further patients are treated, thus assuring maximum early knowledge of any safety concerns. Up to an additional 30 patients will be recruited at each study site, assuming that some screen failures and dropouts will occur, which will still allow us to treat 20 subjects with Leukine® and 20 with placebo, combined for a total of 40 mild-to-moderate AD subjects enrolled from both the UCD and the USF sites.

Data Analysis Plan:

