Primary Endpoint: Generally, descriptive statistics will be utilized to examine safety of participants who received Leukine® injections compared to placebo injections. Safety will be assessed by measuring the toxicity grades of AE’s. These toxicity grades have been standardized by the

National Cancer Institute (NCI) Common Toxicity Criteria for Adverse Events (CTCAE Version 4.03 attached as Appendix E). Differences in toxicity grades will be compared between treatments using a Wilcoxon test for ordered outcome.

Secondary Endpoint and Exploratory Aim 1: Neuropsychological assessments will be graded and scored using the standardized scoring methods associated with each of the neuropsychological tests. Our primary measures for cognitive assessments will be based on the participants' MMSE total score and ADAS-cog total scores. All other neuropsychometry tests will be used secondarily to examine changes in specific cognitive domains. Due to the multitude of both the neuropsychometry tests and the different time points these tests are administered, a Bonferroi correction method will be used to counteract the problem of multiple comparisons.

Tertiary Endpoint: Medial Temporal Lobe Atrophy (MTA) will be assessed using an automated rating system to grade the severity of atrophy in the entire medial temporal region will be employed using the FreeSurfer software automated rating system of individual medial temporal structures, i.e., the Hippocampus (HPC), Entorhinal cortex (ERC) and Perirhinal cortex (PRC), which are specific regions of interest (ROI) in AD pathogenesis. FreeSurfer automatically computes cortical reconstruction and volumetric segmentation, including segmentation of the subcortical white matter and deep gray matter volumetric structures [34] and parcellation of the cortical surface [35] according to a previously published parcellation scheme [36]. This labels cortical sulci and gyri, and thickness values are calculated in the ROIs.

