Once the results are available, if the subject continues to meet entrance criteria they will return for their baseline Day 1 (randomization) visit. This visit takes place about 1 to 4 weeks after the screen visit. At this visit, vital signs are recorded, 33 ml of blood will be drawn for a CBC with differential, a complete metabolic panel (CMP), and for biomarker assays (for example, GM-CSF, IFN- γ , IL-1 β , IL-2, IL-6, IL-8, IL-10, IL-12p70, TNF- α , Eotaxin, IP-10, MCP-1, MCP-4, MIP-1 β , TARC, P-Tau, Total Tau, and A β species), and tests of cognition, such as the MMSE, ADAS-cog, the ADCS-ADL scale, Trails A, Trails B, CDR, and the Mohs Cancellation task, are administered. The test article will then be delivered by the unblinded pharmacist, administered subcutaneously by the (blinded) study nurse or clinician, and the subject then goes home.

Subsequent injections will also be administered at the clinic. About 4 ml of blood will be drawn for CBC plus differential approximately every three days during the treatment phase to monitor for leukocytosis (see safety monitoring plan), and an additional 4 ml of blood will be drawn for CMPs once every week of the treatment phase. Vital signs, injection site review, and adverse events will be recorded at each visit. At the last treatment visit approximately three weeks later, we will record vitals, perform a physical exam, review for adverse events, administer cognitive tests and draw 33 ml blood for a CBC with differential, a CMP, and biomarker assays. A brain MRI will be done for comparison with the initial screen MRI to assess for any changes in the Medial Temporal lobe and for any incidence of vasogenic edema and microhemorrhage.

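### The cognitive power figures assume a single t test at uncorrected alpha .20, but the cognitive comparisons will be Bonferroni-corrected over tests and time points

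*Combined protocol and SAP*

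**What the plan says.** The Sample size considerations section justifies 20 per arm first by the primary safety endpoint. It then gives a table of the "sample size needed per group with alpha at .20 and power at .60 for independent samples t tests", one- and two-tailed, for effect sizes .3, .5, .8 and 1.22. The last is labelled "observed from BMT". The result is used "as a reference to choose an appropriate sample size of AD subjects to receive GM-CSF as a potential cognition enhancer", and the text sums up: "Essentially, only 3-4 subjects are needed for a power of 0.6". The next sentence presents the total of 40 patients as following from this.

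The Data Analysis Plan (Secondary Endpoint and Exploratory Aim 1) says of the same outcomes that, because of the "multitude of both the neuropsychometry tests and the different time points these tests are administered, a Bonferroi correction method will be used". It gives no family-wise alpha, number of comparisons, sidedness or definition of success.

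The possible size of the family comes from elsewhere in the protocol:

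- Specific Aim 2 has cognition "performed at baseline and at approximately 15, 45, and 90 days after initiation", which is three post-baseline visits.
- Hypothesis 2 is to be judged "as measured primarily by MMSE total score and ADAS-cog total score", which is two scales.
- Study Events lists seven instruments: "tests of cognition, such as the MMSE, ADAS-cog, the ADCS-ADL scale, Trails A, Trails B, CDR, and the Mohs Cancellation task".

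**The concern.** A Bonferroni correction over two or more comparisons tests each one below the family alpha. Per-test alpha could stay at .20 only if the family alpha were .40 (two comparisons) or higher, and nothing in the document says so. The table and the 3-4 subjects statement therefore belong to a different analysis from the one planned.

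The practical risk lies in reading the results. The two-tailed entry for a medium effect is 20, which is also the planned arm size, so a reader will take the trial to have .60 power at d = .5. A null corrected result could then be read as evidence against a medium effect, although each comparison had far less power than that.

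**Working it through.** **Inputs.** Table: alpha .20, power .60, independent-samples t test, d = .3, .5, .8, 1.22. Planned size: 20 per arm. The number of comparisons k is my assumption: k = 6 (2 scales × 3 visits) or k = 21 (7 instruments × 3 visits). Family alpha is held at the table's own .20, so per-comparison alpha is .20/6 = .0333 or .20/21 = .0095.

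**Formula.** With n per arm, t has 2n − 2 degrees of freedom and noncentrality d√(n/2). Power is the noncentral-t probability beyond the critical value. For n = 20 and d = .5, this gives 38 df and noncentrality .5 × √10 = 1.58. The two-sided critical values are 1.304 (alpha .20), 2.208 (.0333) and 2.731 (.0095).

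**Reproducing the table.** At alpha .20 and power .60, the smallest n per arm (one-/two-tailed) is:

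| d | Computed | Printed |
|---|---|---|
| .3 | 27/53 | 27/53 |
| .5 | 10/20 | 10/20 |
| .8 | 4/8 | 4/8 |
| 1.22 | 2/4 | 3/4 |

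Seven of eight cells match. In the eighth, n = 2 just reaches 60.3%, so the printed 3 is conservative.

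**Power for any one comparison at 20 per arm, family alpha .20.**

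| d | Sides | Uncorrected | k = 6 | k = 21 |
|---|---|---|---|---|
| .5 | two | 61% | 28% | 14% |
| .8 | two | 89% | 63% | 43% |
| 1.22 | two | 99% | 95% | 86% |
| .5 | one | 77% | 39% | 21% |
| .8 | one | 95% | 74% | 54% |

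**n per arm for 60% power.**

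| d | Sides | Uncorrected | k = 6 | k = 21 |
|---|---|---|---|---|
| 1.22 | two | 4 | 9 | 13 |
| 1.22 | one | 2 (printed 3) | 7 | 11 |
| .5 | two | 20 | 47 | 67 |
| .5 | one | 10 | 36 | 56 |

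**The 3-4 subjects statement, d = 1.22.** Three per arm one-tailed falls from 72% to 26% (k = 6) or 10% (k = 21). Four per arm two-tailed falls from 63% to 24% or 10%. With only two comparisons the figures are 52% and 45%, already below .60.

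**If success means at least one significant comparison.** I simulated 200,000 trials per scenario at d = .5 with 20 per arm, assuming a common effect and equal correlations of .5 or .7 between outcomes. Success was at least one Bonferroni-significant result in the favourable direction.

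| k | Two-sided | One-sided |
|---|---|---|
| 6 | 55–65% | 68–77% |
| 21 | 49–64% | 61–75% |

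**If family alpha were .05 instead (two-sided, 20 per arm).** Only the step from the second column to the third and fourth is due to Bonferroni.

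| d | Uncorrected .05 | k = 6 | k = 21 |
|---|---|---|---|
| .5 | 34% | 13% | 6% |
| .8 | 69% | 41% | 26% |
| 1.22 | 96% | 85% | 72% |

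**The case against.** The best defence is that little hangs on these figures. The trial is a pilot, cognition is secondary, and 20 per arm rests first on safety. The cognition argument leans on the transplant effect of 1.22, at which 20 per arm is ample after any correction considered here. No sentence sets .60 power at a medium effect as a target. All of this stands, and it limits the consequence. It does not rescue the 3-4 subjects statement, which is made at d = 1.22 and fails there with as few as two comparisons. That effect also comes from transplant patients, and the table itself offers smaller effects as planning cases.

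The loss also depends on choices the plan leaves open. At d = .5, two-sided power is 46% with k = 2 and 39% with k = 3, and one-sided power with k = 6 is 39%. At d = .8, k = 6 still meets .60. If any significant comparison counts as success, .60 may be met even at d = .5. These points are right, and they are why the figures above are ranges. They do not make the uncorrected table a description of the corrected analysis.

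Finally, the Data Analysis Plan names the t test only as one that may be used, so a corrected t-test calculation could still miss the eventual analysis. That is a reason to name the test when power is restated.

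**Conclusion.** The concern holds. The stated sample sizes, and the 3-4 subjects conclusion, are correct only for one t test at alpha .20, whereas the plan tests cognition at a Bonferroni-corrected level. With 20 per arm, two-sided tests and family alpha .20, power for any one comparison at d = .5 is 28% (k = 6) or 14% (k = 21), against the 61% that the table implies. At d = .8 it is 63% or 43%, against 89%.

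The conflict itself needs only two or more comparisons. Its size rests on the assumed family, family alpha and sidedness. The shortfall at d = .5 applies to each comparison separately and is not established if any significant comparison counts as success. The safety justification and the enrolment target are not affected. This should be fixed because a stated figure is wrong for the planned analysis and correcting it is cheap.

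**What to change.** In the Sample size considerations section:

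1. Delete the sentence saying that 3-4 subjects suffice for a power of 0.6.
2. Label the table as single-test figures without multiplicity correction.
3. Restate power at 20 per arm at the Bonferroni-corrected level. This means fixing, before unblinding, the family of comparisons, family-wise alpha, sidedness, test and definition of success.

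As an alternative to item 3, state that the cognitive analysis is not powered for small or medium effects.

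The cost is text only, with no added patients, visits or data, although item 3 also requires analysis decisions that the plan has not yet recorded. The stated power becomes less favourable. Narrowing the family to two scales at one visit is not needed for this fix. At .20/2 and d = .5, two-sided power is 46% per comparison and 59–63% for any success, hardly different from the 55–65% with six comparisons.

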In the first experiment, 5 μ g bolus injections of M-CSF, G-CSF, and GM-CSF were injected into the hippocampus of the ipsilateral brain hemisphere with vehicle, artificial cerebrospinal fluid (aCSF), injected into the contralateral hippocampus as a control in aged cognitively-impaired transgenic AD (PS/APP) mice [2]. The mice were then sacrificed one week later and analyzed. While M-CSF injection resulted in significant hyperplasia to the treatment hemisphere and no effect on amyloid deposition, G-CSF showed a modest reduction in amyloid deposition in the injected side. This outcome was confirmed by colleagues using daily peripheral G-CSF injections, which also led to reduced amyloidosis and cognitive deficits in the Radial Arm and Morris Water Mazes [16]. In contrast to the mild G-CSF effect, our GM-CSF injections, demonstrated pronounced decreases in amyloid deposition, as compared to control hemispheres (Fig 1a). Anterior to posterior quantification of amyloid plaques revealed significant reductions within individual mice and overall significant reductions for all plaque parameters measured (Fig 1b).

[figure not shown]

Figure 1. Intra-hippocampal injection of GM-CSF on left and artificial cerebrospinal fluid (aCSF) on right. (a) Representative coronal tissue cryo-sectioned at 14 μm and stained with MabTech $\alpha\text{-A}\beta$ /Alexa 546. Image is a montage of about 145 pictures taken at 10X. (b) Overall plaque reductions seen in all 4 plaque parameters measured from 5 quantified sections per mouse ($n = 4$ mice). Area and Perimeter data were calculated from the total number of plaque values in each hemisphere per section, and Feret Diameter and Integrated Density were calculated from the average values of the plaques measured in each hemisphere per section. (Area: $p < 1.11\text{E-}07$; Perimeter: $p < 1.41\text{E-}06$; Feret Diameter: $p < 2.36\text{E-}09$; Integrated Density: $p < 1.11\text{E-}07$)

Daily subcutaneous injection of GM-CSF:

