Before initiation of the current trial at the UCD site, fourteen participants enrolled in a preliminary study at USF. Of these 14 participants, 9 completed the entire study, including both follow-up visits; and the other 5 completed all treatment visits and at least one of the follow-up visits. Also, 3 of the 14 participants may have received the full Leukine® dose, but this number cannot be definite due to blinding of the study team at USF. Finally, the only AE's reported include injection site reactions seen in 6 patients (redness, raised, itching, bruising). No serious AE's were reported in these 14 participants.

The current trial (COMIRB #12-1273) was originally approved as a multi-site trial with recruitment efforts again, at USF, in Tampa, FL. USF's recruitment yielded 5 subjects who were enrolled into the current trial. Two of these subjects were screen failures and three completed the trial at USF. USF's last subject officially completed the trial on June 12th, 2015. However, due to USF's low recruitment, the decision was made to amend the protocol and close USF as a site. This amendment was approved by COMIRB on July 25th, 2016. Since the closure of the USF site, the research team at UCD has received all pertinent study data and study samples via secure HIPAA compliant practices.

[figure not shown]

Figure 4. Total Neuropsychological Performance in Hematopoietic Cell Transplant (HCT) Recipients Receiving GM-CSF+G-CSF versus G-CSF Only.

The GM-CSF+G-CSF group performed significantly better at 6 months post-HCT ($p=.04$), but there were no group differences at 12 months post-HCT ($p=.24$). The GM-CSF+G-CSF group improved significantly from baseline to 6 months post-HCT ($p=.01$) and from baseline to 12 months post-HCT ($p<.01$). The G-CSF group demonstrated no change from baseline to 6 months post-HCT ($p=.33$) but significant improvement from baseline to 12 months post-HCT ($p<.01$). Note: No patients received GM-CSF only. (GM-CSF: Granulocyte-Macrophage Colony-Stimulating Factor; G-CSF: Granulocyte Colony-Stimulating Factor)

EXPERIMENTAL DESIGN AND METHODS:

Recruitment:

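### The 3-4 subject sizing statement rests on a transplant-study effect for GM-CSF added to G-CSF, which is not an estimate for Leukine alone versus placebo in Alzheimer's disease

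*Combined protocol and SAP*

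**What the plan says.** Specific Aim 2 runs a cognitive battery at baseline and at about 15, 45 and 90 days, "to determine whether any AD features reverse during or after Leukine[®] treatment compared to subjects receiving placebo". MMSE and ADAS-cog are the main measures. The two arms are placebo and full-dose Leukine, 20 each. G-CSF is given in neither.

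Sample size considerations first calls 20 per arm adequate for the primary safety endpoint. It then turns to cognition and cites a bone marrow transplant (BMT) study with "19 patients receiving GM-CSF plus G-CSF, compared to patients receiving only G-CSF", while acknowledging that the study was not designed for that comparison. A table follows, giving the "sample size needed per group with alpha at .20 and power at .60 for independent samples t tests". Three of its rows are generic effect sizes (0.3, 0.5, 0.8). The fourth is "1.22 – observed from BMT", with 3 per group one-tailed and 4 per group two-tailed.

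The text then treats the BMT effect as the reference for choosing the number of AD subjects, states "Essentially, only 3-4 subjects are needed for a power of 0.6", and moves to a total of 40. The Dosage section repeats the add-on comparison and says that it made the power analysis possible. The Figure 4 legend records: "Note: No patients received GM-CSF only".

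**The concern.** A power figure belongs to a particular contrast, population, outcome and time point. Neither arm of the study that supplied the 1.22 exists in this trial: its test arm was GM-CSF plus G-CSF and its control was G-CSF. The statement about 3-4 subjects is nevertheless made without qualification about AD subjects receiving GM-CSF.

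At stake is what a reader takes the trial to be able to detect. Set beside 3-4, 20 per arm looks several times larger than the cognition endpoint needs. On the table's own medium row (0.5, two-tailed) the requirement is exactly 20 per group, so there is no surplus.

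**Working it through.** **Inputs from the documents.** Alpha .20, power .60, independent-samples t test, effects 0.3, 0.5, 0.8 and 1.22 (Sample size considerations). 20 per arm, 1:1 (same section). Bonferroni correction over cognitive tests and time points, with neither the number of tests nor the starting alpha given (Data Analysis Plan).

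**1. The plan's own figure.** For n per group and standardized effect d, the degrees of freedom are 2n − 2 and the noncentrality is d√(n/2). Two-sided power is P(|T| > c), where T is noncentral t and c is the 1 − α/2 quantile of the central t.

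- d = 1.22, n = 4, two-tailed: noncentrality 1.22 × √2 = 1.725, c = 1.440 on 6 df, power 0.63.
- d = 1.22, n = 3, one-tailed: noncentrality 1.22 × √1.5 = 1.494, c = 0.941 on 4 df, power 0.72. Two per group would already give 0.60.
- d = 0.5, n = 20, two-tailed: noncentrality 0.5 × √10 = 1.581, c = 1.304 on 38 df, power 0.61.

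Every stated group size in the table gives at least 60% power, and only the 1.22 one-tailed entry is larger than the minimum (3 against 2). The arithmetic is not the problem. The counts are per group, so 3-4 means 6-8 subjects in total.

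**2. Where the input comes from.**

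| | Source of 1.22 | This trial |
|---|---|---|
| Test arm | GM-CSF + G-CSF | Leukine (GM-CSF) alone |
| Control | G-CSF | Placebo |
| Population | Transplant patients | Mild-to-moderate AD |
| Design | Retrospective | Randomized, blinded |
| Outcome | Total neuropsychological z score | MMSE, ADAS-cog |
| Timing | 6 and 12 months | About 15, 45 and 90 days |

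Write μ for the mean outcome. The source estimates [μ(GM+G) − μ(G)]/SD in its own population. The trial needs [μ(GM) − μ(placebo)]/SD in AD. The two agree only if GM-CSF acts equally with and without G-CSF, and if the effect relative to the SD is also the same in the other population, on the other scale and at the other times. The documents neither state nor argue any of these conditions.

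**3. What 20 per arm gives.** The documents hold no estimate for GM-CSF alone versus placebo in people, so the table's generic rows serve as an assumed range. One two-sided t test, n = 20:

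| Alpha | c (38 df) | d = 0.3 | d = 0.5 | d = 0.8 |
|---|---|---|---|---|
| .20, uncorrected | 1.304 | 38% | 61% | 89% |
| .20/6 | 2.208 | 11% | 28% | 63% |
| .05/6 | 2.784 | 4% | 13% | 41% |

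The divisor 6 is an assumption: 2 main measures × 3 post-baseline visits. Without correction, 60% power at alpha .20 two-sided needs d of about 0.49.

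**4. How 1.22 was obtained.** The Figure 4 legend gives between-group p = .04 at 6 months and p = .24 at 12 months. Taking p = .04 as if from a t test with 19 treated patients gives d = t√(1/19 + 1/m). With m = 19 controls that is 2.131 × 0.324 = 0.69; with m = 300 it is 2.062 × 0.237 = 0.49. The source used Kruskal-Wallis tests and m is assumed, so this is only a rough guide. It shows that 1.22 fits poorly with the reported between-group result, and that one cannot say from these documents exactly what 1.22 measures.

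**The case against.** The strongest reply is that nothing in the design depends on the number. Twenty per arm is first justified by safety, the trial is called a pilot, the BMT effect is called a reference for a secondary endpoint, and 3-4 subjects could not arithmetically lead to 20 per arm. The source contrast is also disclosed in several places, and the table already shows smaller effects. All of this stands, and it limits the point to the stated cognitive power. It does not rescue the sentence itself, which uses only the 1.22 row and carries no caveat.

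A second reply is that G-CSF was common to both source groups, so the add-on comparison isolates the GM-CSF increment unless the two drugs interact. That is correct. The documents give no evidence of interaction, but none of its absence either, and the differences in population, outcome and timing remain.

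A reader might go further and infer that the source control was active, so that 1.22 is biased in a known direction. The Preliminary Preclinical Results do report "daily peripheral G-CSF injections, which also led to reduced amyloidosis and cognitive deficits" in mice, and the G-CSF-only group improved by 12 months. That gain is an uncontrolled within-group change, however, and the same group showed no change at 6 months (p = .33). Recovery after transplant would explain it equally well. The direction of any bias is unknown.

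**Conclusion.** The 3-4 subject statement has no support for this trial's contrast and should not stand as a statement about its power. It rests on GM-CSF added to G-CSF in transplant patients, not on Leukine against placebo in AD.

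Two stronger inferences are not supported. First, this does not show that 20 per arm is wrong, because that number rests on the safety endpoint. Second, the gap between power at 1.22 and at 0.5 (99% against 61% with 20 per group) does not measure the harm done by the mismatch. It follows from choosing 0.5, and the true effect is not in the documents.

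What can be said is conditional. At 20 per arm, power runs from 38% to 89% over effects of 0.3 to 0.8 for one uncorrected two-sided test at alpha .20. With six tests assumed, it runs from 11% to 63% at .20/6, or from 4% to 41% at .05/6. No rule for reading a null cognitive result is written, so the risk of over-reading one is a reason for clear wording and not a demonstrated error.

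**What to change.** In Sample size considerations, delete the sentence "Essentially, only 3-4 subjects are needed for a power of 0.6" and the sentence before it that makes the BMT effect the reference for the AD sample size. Delete the 1.22 row, or mark it as coming from the transplant study and not an estimate for Leukine versus placebo in AD. The label should not claim more about how 1.22 was derived unless the sponsor confirms it. In Dosage, drop the sentence saying that the BMT comparison made the power analysis possible.

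Suggested replacement:

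> No estimate of GM-CSF alone versus placebo was available. With 20 per arm, a single two-sided t test at alpha .20, before any multiplicity correction, has about 61% power for an assumed standardized difference of 0.5, 89% for 0.8 and 38% for 0.3; power is lower under the planned Bonferroni correction.

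Then add the power at the corrected alpha, once the number of tests and the starting alpha are fixed. The six-test figures above are only an illustration. Keep 20 per arm.

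The cost is wording in two sections and a less favourable stated power. No patients, visits or procedures are added.
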